The main potential side effects with the use of CyA are increases in blood pressure due to nephrotoxicity. Follow up of 42 paediatric patients with severe atopic eczema in a randomised controlled trial using continuous (n=21) vs repeated burst treatment (n=21) with 5mg/kg/day of CvA found no clinically significant change in mean serum creatinine or blood pressure over a 12 months period and tolerability was considered either 'good' or 'very good' in 80% of patients (11). The main reported side effects were: nausea (n=8), paraesthesia (7), hypertrichosis (5), swollen gums (4), headache (4), rhinitis (3), upper respiratory tract infection (3), abdominal pain (3), and hyperuricaemia (11). The only RCT that used CyA (vs. MTX) in children with severe atopic eczema found the following side effects over a 12 weeks treatment period: nausea/vomiting (2/20), glossitis/oral ulceration (1/20), diarrhoea (3/20), pancytopenia (3/20), anaemia (4/20), leukopenia (7/20), thrombocytopenia (2/20), abnormal liver profile (2/20), abnormal renal function (3/20), and hypertension (1/20). Regular blood pressure and renal function measurements are the main safety investigations in the CyA arm of the study. To provide an assessment of renal function above and beyond standard NHS care, we are not only determining plasma creatinine but also cystatin C levels (baseline, 2 weeks, 8 weeks, 12 weeks, 36 weeks and 60 weeks) as well as urinary tubular N-acetylbeta-D-glucosaminidase (at baseline, 2 weeks, 12 weeks, 36 weeks and 60 weeks).

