As for MTX, gastrointestinal disturbance, in particular nausea, liver function abnormalities and bone-marrow suppression are the main potential side effects, but the medication is well tolerated in the majority of cases and considered safe in the long-term, partly based on the extensive rheumatology and gastroenterology experience in children, using similar if not higher doses for longer periods of time and often in combination with biologics (4, 5, 20-23). In addition, the only RCT using MTX in children with severe atopic eczema over a 12 week period, the following adverse events were recorded: nausea/vomiting (4/20), abdominal pain (1/20), glossitis/oral ulceration (4/20), diarrhoea (5/20), pancytopenia (1/20), anaemia (6/20), leukopenia (2/20), abnormal liver function (5/20), abnormal renal function (1/20), fatique (6/20), headache (3/20), and flu-like symptoms (1/20). This overall favourable side effect profile has been confirmed by three observational studies, involving a total of 102 paediatric patients with treatment durations of up to 38 months (24-26). We are performing safety bloods after the initial test dose for MTX to capture rare idiosyncratic reactions early and review participants in both study arms with safety bloods and enquiry about adverse events fortnightly for the first month, then monthly until week 12 and then eight-weekly, while on treatment, in keeping with the American Academy of Dermatology guidelines for the use of these systemic agents in children with severe atopic eczema(27). Patients are also encouraged to contact the study team in case of any concerns about drug adverse reactions

between study visits. In addition, all potential participants and their parents will be informed about common and rare serious side effects in the Patient Information Leaflets and also instructed to contact the study team/seek medical advice straight away if any of the following occur:

Methotrexate:

- Infections, including fever (temperature above 38°C), chills, sore throat or chicken pox
- Skin rash, changes in nail or skin colour, or skin ulcers
- Jaundice
- Bleeding gums, unexpected bruising or bleeding that doesn't stop as quickly as normal
- Melaena
- Chest pain, difficulty breathing or chronic dry cough
- Severe and continuing diarrhoea, vomiting or stomach pains

Ciclosporin:

- Infections, including fever (temperature above 38°C), chills, sore throat or chicken pox
- Unusual bleeding that is difficult to stop
- Severe bruising

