6.4.2 Blinding

As the trial interventions are at different frequencies (daily vs once weekly), have rather different side effect profiles and since no placebo is used as part of the study, blinding of the local investigator and research nurse will not be possible. However, the assessor who will perform the severity assessments (o-SCORAD, EASI & IGA), will be blinded to the trial allocation. The following steps are in place to ensure blinding is maintained:

- -All severity assessments will be conducted by an independent member of the research team, who has no direct involvement or other contact with the trial participants.
- Participants will be reminded in their study visits not to mention the treatment they are on to the independent member of the research team carrying out the assessments.
- The blinded assessor will wear a badge at the severity assessment, reminding participants not to mention what treatment they are on.
- All questions relating to the acceptability and use of the trial drugs will be completed in a patient diary that will be returned to the study research nurse.
- Dispensing of study drugs will be completely independent from the blinded assessor.

Following each severity assessment, the blinded assessor will be asked whether they had become unblinded to the allocation and this information will be recorded in the Case Report Form. If the blinded assessor does become unblinded, this will be used to inform a sensitivity analysis.

Whilst it will not be possible to blind participants to their treatment allocation either, efforts will be made to minimise expectation bias by emphasising in the trial literature that there is currently no strong evidence favouring either drug choice in severe atopic eczema in children.

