- b. The number of flares, side effects and adverse events during treatment will be captured through questionnaires administered by the research nurses and through a diary collected by the patient or parent/guardian.
- c. Child and parental QoL (CDLDI/IDQOL/DFI) & CHU-9D will be assessed at baseline, 12, 36, 48 and 60 weeks.
- d. Blood for drug metabolite/trough levels will be taken at 2, 8, 12, 36 weeks.
- e. Blood and tape strips for mechanistic work will be taken at baseline, 12, 36, and 60 weeks. Mechanistic blood samples and tape strip samples will only be collected from patients recruited at St Thomas' Hospital.
- f. A blood sample will be collected at the week 0 visit for filaggrin analysis. If a blood sample cannot be collected a saliva sample will be used for this analysis.
- g. AE and SAE data will be collected, until 4 weeks after treatment has stopped.

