9.5 Secondary Endpoint(s)

- 1. Change in atopic eczema severity using the EASI, IGA, o-SCORAD and POEM between baseline and 12, 36, 48, and 60 weeks.
- 2. Number of flares in each study arm as well as the proportion of children who re-flared following treatment cessation.
- 3. Proportion of participants achieving 50% improvement in the o-SCORAD index at 12, 36, 48, and 60 weeks.
- 4. Proportion of participants who withdraw from treatment because of AEs.
- 5. Disease-specific patient and parental quality of life (QoL) measured with the CDLQI/IDQOL and DFI scores between baseline and 12, 36, 48 & 60 weeks.
- 6. Assess the cost-effectiveness of CyA vs MTX, based on utility measured using the CHU-9D.
- 7. Immuno-metabolic effects of MTX and CyA, especially in relation to markers of glycolytic activation and T cell cytokine signature, at baseline, during treatment and post treatment cessation.
- 8. Drug-related side effects of both MTX and CyA and their association with MTX polyglutamate and CyA trough levels.
- 9. The association between MTX polyglutamate and CyA trough levels and treatment response (reduction in disease severity).

10. The association between FLG carriage (yes/no) and treatment response.

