10.4 Relationship to Trial Treatment

The assignment of the causality should be made by the investigator responsible for the care of the participant using the definitions in table 9.

If any doubt about the causality exists the local investigator should inform the study coordination centre who will notify the Chief Investigator. In the case of discrepant views on causality between the investigator and others, the MHRA will be informed of both points of view.

Table 10: Definitions of Causality

Relationship	Description			
Unrelated	There is no evidence of any causal relationship. N.B. An			
	alternative cause for the AE should be given			
Unlikely	There is little evidence to suggest there is a causal relationship			
	(e.g. the event did not occur within a reasonable time after			
	administration of the trial medication). There is another			
	reasonable explanation for the event (e.g. the participant's clinical			
	condition, other concomitant treatment).			
Possibly	There is some evidence to suggest a causal relationship (e.g.			
	because the event occurs within a reasonable time after			
	administration of the trial medication). However, the influence of			
	other factors may have contributed to the event (e.g. the			
	participant's clinical condition, other concomitant treatments).			
Probably	There is evidence to suggest a causal relationship and the			
	influence of other factors is unlikely.			
Almost certainly	There is clear evidence to suggest a causal relationship and other			
	possible contributing factors can be ruled out.			

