Staff at the CTRC will liaise with the Chief Investigator (or designated other specified in the protocol) who will evaluate all SAEs received for seriousness, expectedness and causality. Investigator reports of suspected SARs will be reviewed immediately and those that are SUSARs identified and forwarded to Kings Health Partners Clinical Trials Office for onward reporting to the regulatory authority. The CTRC will be responsible for onward reporting to the MREC of any SUSARs. The causality assessment given by the Local Investigator at the hospital cannot be overruled and in the case of disagreement, both opinions will be provided with the report.

The PIs at all institutions participating in the trial will be notified of any SUSARs. Patient safety incidents that take place in the course of research should be reported to the National Patient Safety Agency (NPSA) by each participating NHS Trust in accordance with local reporting procedures.

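### Secondary endpoint 8 words the only general toxicity outcome as drug-related side effects, and no source of that judgement is blinded; the between-arm comparison should rest on all adverse events

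*Protocol*

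**What the plan says.** Section 9.5, item 8, gives the toxicity endpoint as "Drug-related side effects of both MTX and CyA and their association with MTX polyglutamate and CyA trough levels"; the protocol summary (section 1) words it the same way. Objective 8 in section 2.3 is to compare the toxicity profiles of the two drugs. The only other listed endpoint built on adverse events is withdrawal from treatment because of them (section 9.5, item 4).

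On attribution, section 10.4 states: "The assignment of the causality should be made by the investigator responsible for the care of the participant". Section 10.5 counts an event as a drug reaction when that investigator grades it possibly, probably or almost certainly related. Section 6.4.2 says that "blinding of the local investigator and research nurse will not be possible", and limits the blinded assessor to o-SCORAD, EASI and IGA. Section 8.1.1 says that "side effects and adverse events during treatment will be captured through questionnaires administered by the research nurses", and also through a diary.

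Section 10.8 requires investigators to report every adverse event whatever its cause, and section 10.7 sets the period from randomisation to four weeks after treatment stops.

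**The concern.** Randomisation makes the arms comparable for all events. It does not do so for events picked out afterwards by someone who knows which drug the child took.

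The protocol also says what to expect of each drug. For ciclosporin (CyA), section 2.4 says: "The main potential side effects with the use of CyA are increases in blood pressure due to nephrotoxicity". For methotrexate (MTX), it says that "gastrointestinal disturbance, in particular nausea, liver function abnormalities and bone-marrow suppression are the main potential side effects". The same bout of nausea could be called related more often on MTX, and the same rise in blood pressure more often on CyA. These shifts would run in opposite directions by organ class. They would therefore distort mainly the organ-class profile, which is what a clinician choosing between the drugs will read. Section 2.4 itself ranks patient safety as an important secondary outcome.

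The drug-related restriction does suit the second half of the endpoint, the association with drug levels. It is the comparison between arms that it serves badly.

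**Working it through.** The protocol gives no figure to reproduce here, so the check has two parts.

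**1. Is there a blinded route to drug-related status?**
- Investigator grading (10.4, 10.5): the investigator knows the arm (6.4.2, 7.4, 10.8.1).
- Nurse questionnaires (8.1.1): nurses know the arm (6.4.2, 7.4).
- Patient or parent diary (8.1.1, 8.1.2): participants know the arm (6.4.2, 7.4).
- Blinded assessor (6.4.2): severity scores only.
- Chief Investigator review (10.9): serious events only.

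Section 9.5 does not say which source feeds endpoint 8, but none of them gives a blinded attribution.

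**2. How large could the effect be?**

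Inputs:
- 51 children per arm (9.6), with no allowance for loss.
- Event rates in the paediatric trial cited in 2.4.1, which run from 1/20 (5%) to 7/20 (35%).
- Assumed, not in the protocol: the attribution rates, Fisher's exact test and a two-sided 0.05 level. Section 9.7 plans relative risks (RR) with 95% intervals for binary secondary outcomes, so the RR is the more direct measure.

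*Single event type, equal true risk.* Apparent rate = true risk × attribution rate. The rejection probability is summed exactly over both binomial distributions.

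| True risk | 50% v 50% | 60% v 50% (RR 1.2) | 80% v 50% (RR 1.6) |
|---|---|---|---|
| 10% | 0.8% | 1.1% | 2.9% |
| 20% | 1.8% | 2.6% | 8.2% |
| 35% | 2.7% | 4.4% | 18% |

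*At least one related event.* P = 1 − exp(−m × attribution), where m is events per child. The counts listed in 2.4.1 sum to 28/20 = 1.40 for CyA and 39/20 = 1.95 for MTX; each m is used in turn for both arms.
- 80% v 50% for all events, m = 1.40: 67.4% v 50.3%, RR 1.34.
- 80% v 50% for all events, m = 1.95: 79.0% v 62.3%, RR 1.27.
- Half the events at 80% v 50% and half at 50% v 80%: 59.7% in both arms (m = 1.40) or 71.8% in both (m = 1.95), RR 1.00. The organ classes underneath show RR 1.6 and 0.5/0.8 = 0.63.

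*Hiding a true difference.* The cited trial's leukopenia rates are 7/20 (35%) on CyA and 2/20 (10%) on MTX. Fisher p = 0.13 in that trial, so this is an illustration only.

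| Attribution CyA / MTX | Apparent rates | RR | Power |
|---|---|---|---|
| All causes | 35% v 10% | 3.5 | 83% |
| 50% / 50% | 17.5% v 5% | 3.5 | 38% |
| 50% / 60% | 17.5% v 6% | 2.9 | 31% |
| 50% / 80% | 17.5% v 8% | 2.2 | 20% |
| 80% / 80% | 28% v 8% | 3.5 | 69% |
| 80% / 90% | 28% v 9% | 3.1 | 63% |

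The fall from 83% to 38% comes from discarding events at 50% attribution, equally in both arms. Differential attribution accounts only for the further fall to 31% or 20%, and for the drop in RR. With a higher base attribution the whole effect shrinks.

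*Cost of counting all causes.* Take true drug effects of 20% v 10% and add a 20% background risk in each arm: 1 − 0.8 × 0.8 = 36% and 1 − 0.9 × 0.8 = 28%. RR falls from 2.0 to 1.29, and power from 20% to 10%.

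**The case against.** The strongest reply is that sections 9.1 and 9.7 leave detail to an analysis plan that is not shown, and that plan may well tabulate all adverse events. Nothing in the protocol forbids it. This stands as a limit: a reader might infer that the protocol confines safety analysis to drug-related events, and it does not. But the restriction is written into the named endpoint, so an all-event comparison would be an addition to the listed endpoints.

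Second, section 9.5 does not tie endpoint 8 to the section 10.4 grading. That is correct; the link is the natural reading and is not stated. The alternative sources are open-label as well, so the point does not depend on it.

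Third, section 10.9 says "The causality assessment given by the Local Investigator at the hospital cannot be overruled". A reader might infer that the site's view is final for the endpoint. It is not shown to be: the sentence belongs to serious-event and SUSAR reporting, where the Chief Investigator also judges causality and both opinions are forwarded if they differ.

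Fourth, Tables 5 and 8 require eGFR, blood-pressure, liver, platelet and neutrophil events to be recorded as adverse events at the same limits in both arms, and a grade of possibly is enough to count as related. Both make large attribution gaps less likely. They do not remove the filter, because a recorded event would still have to be judged drug-related to enter endpoint 8.

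Fifth, counting all causes has its own price. It dilutes true effects, and the MTX arm alone has a week 1 visit with adverse-event enquiry and safety bloods (Table 9; section 8.1.2), which adds ascertainment in that arm. This stands too, and is the reason to keep related events as a supportive analysis.

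**Conclusion.** The point holds as a minor one. The endpoint matching a between-arm toxicity objective is restricted by a judgement that the protocol gives no blinded way to make, although unrestricted data are already collected. The size rests entirely on assumed attribution rates. It is negligible at 60% against 50%, and matters only for gaps of the order of 80% against 50%, and then chiefly within organ classes. The protocol does not show that such gaps will occur. Nor do the leukopenia figures show that biased attribution would by itself hide a true difference, since most of that power loss comes from discarding events. All-event counting removes the attribution step but not open-label reporting.

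**What to change.** Reword endpoint 8 (section 9.5, and the summary in section 1) in two parts:

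1. The between-arm safety comparison uses all adverse events regardless of attributed cause: children with at least one event, by organ class and by severity, and serious events.
2. Drug-related events, and their association with MTX polyglutamate and CyA trough levels, are a supportive analysis, with the source of the relatedness judgement named.

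The cost is the rewording of one secondary endpoint. No visit, form or sample-size change follows, because all events are already reported in both arms. When results are read, the dilution by background illness and the extra week 1 enquiry in the MTX arm should be stated.

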9.6 Sample Size

For the first primary outcome (o-SCORAD), the change from baseline to 12 weeks will be calculated for each participant. The study aims to detect a difference of 8 o-SCORAD points, assuming a standard deviation (SD) of 10 (based on the only other paediatric RCT with systemic immunosuppressive medication in children (7), which saw a SD of 6.3 (MTX arm) vs 8.9 (CyA arm) at 12 weeks) a sample size of 41 per group, increasing to 49 per group to allow for an estimated 18% loss to follow up, will be required to provide 90% power using a t-test with a 0.025 two-sided significance level. Our assumption of 8 Units in the o-SCORAD index representing the minimal clinically important difference between treatments is based on calculations from three other RCTs with immuno-suppressive medication in children and adults with severe atopic eczema (33).

The co-primary outcome of this trial is time to first significant flare after treatment cessation (return to baseline o-SCORAD (or worse) or re-starting systemic treatment), as this may be an important factor influencing potential change in prescribing behaviour. The number of patients on CyA burst treatment who went into remission after the first three months of treatment in the study by Harper et al was three out of 21, indicating that 86% of patients reflared. Assuming a similar flare risk in our CyA group, a sample size of 43 in each group (51 in each group with estimated loss to follow up of 18%) will have 80% power to detect a reduction in re-flare of 30% (from 86% to 56%) using a two-sided test with a 0.025 significance level.

Randomising a total of 102 participants, 51 into each of the study arms, satisfies both sample size calculations.

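### Section 9.6: with the assumed 18% loss, 51 per arm leaves 41.8 children, short of the 43 the flare calculation requires (minor)

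*Protocol*

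**What the plan says.** Protocol section 9.6 (Sample Size) makes two calculations, one per co-primary endpoint.

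- **o-SCORAD change at 12 weeks:** difference 8, SD 10, 90% power, t-test at two-sided 0.025. This gives 41 per group, "increasing to 49 per group to allow for an estimated 18% loss to follow up".
- **Time to first significant flare:** the ciclosporin flare risk comes from an earlier paediatric study of burst treatment, in which the number in remission "was three out of 21, indicating that 86% of patients reflared". The text then gives "a sample size of 43 in each group (51 in each group with estimated loss to follow up of 18" per cent, which "will have 80% power to detect a reduction in re-flare of 30% (from 86% to 56" per cent, "using a two-sided test with a 0.025 significance level".

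The section closes: "Randomising a total of 102 participants, 51 into each of the study arms, satisfies both sample size calculations".

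**The concern.** The flare calculation states a required number (43 per arm), a loss rate (18%) and a randomised number (51 per arm). These three cannot all hold, because removing 18% of 51 leaves fewer than 43. The closing sentence of section 9.6 is the protocol's justification for the number of children randomised, and it covers both co-primaries.

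Two things are at stake, both modest. Flare is the endpoint planned at the lower power (80% against 90%), so a shortfall falls where the stated margin is thinner. In addition, retention could run at the planned 18% and look adequate while the evaluable number sits below the stated requirement. The only sample-size check in section 9.7 concerns the o-SCORAD standard deviation and would not show this.

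**Working it through.** **Inputs (all section 9.6).** Flare: p1 = 0.86, p2 = 0.56, two-sided alpha 0.025, power 80%, 43 per arm raised to 51. o-SCORAD: difference 8, SD 10, two-sided alpha 0.025, power 90%, 41 per arm raised to 49. Loss 18%. Total 102, allocated 1:1.

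**Step 1. Reproduce 43.** Two-proportion formula with pooled variance under the null and no continuity correction:

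n = [z(0.9875) × √(2·p̄·(1 − p̄)) + z(0.80) × √(p1(1 − p1) + p2(1 − p2))]² / (p1 − p2)²

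with p̄ = 0.71, z(0.9875) = 2.241 and z(0.80) = 0.842:

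n = [2.241 × √0.4118 + 0.842 × √0.3668]² / 0.09 = 42.17, rounded up to **43**. The base figure is right.

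**Step 2. Reproduce 41.** Noncentral t: power is 89.9% at 40 per arm and 90.7% at 41; the unrounded requirement is 40.07. Rounded up, **41**. This is also right.

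**Step 3. Apply 18% loss to the randomised numbers.**

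- Flare: 51 × 0.82 = **41.8**, below 43 and below 42.17. Rounding 43 up does not explain the gap.
- o-SCORAD at its own figure: 49 × 0.82 = **40.2**, below the stated 41, though just above the unrounded 40.07.
- o-SCORAD at the number actually randomised: 51 × 0.82 = 41.8, above 41.

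**Step 4. Inflate the stated requirements so that 18% loss leaves them intact (divide by 1 − 0.18).**

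- Flare: 43 / 0.82 = 52.4, so 53 per arm, 106 in total.
- Flare, aiming only for 80% power: 42.17 / 0.82 = 51.4, so 52 per arm, 104 in total.
- o-SCORAD: 41 / 0.82 = 50 per arm.

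**Step 5. Loss that 51 per arm tolerates.** (51 − 43) / 51 = 8/51 = **15.7%** for flare; (51 − 41) / 51 = 19.6% for o-SCORAD.

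**Step 6. Power at 18% loss.** Flare, same formula as step 1:

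- 43 per arm: 80.9%
- 42 per arm: 79.8%
- 41.8 per arm: **79.6%**
- 41 per arm: 78.7%

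o-SCORAD at 41.8 per arm: 91.3%.

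**Step 7. Where 51 and 49 might come from.** 43 × 1.18 = 50.7, rounded up to 51; 41 × 1.18 = 48.4, rounded up to 49. Both stated figures match. However, dividing the unrounded numbers by 0.82 and rounding to the nearest integer gives the same pair: 42.17 / 0.82 = 51.4, to 51; 40.07 / 0.82 = 48.9, to 49. The figures alone cannot separate the two routes.

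**Step 8. The test that will be used.** Section 9.7 compares time to flare by log-rank and survival regression, not by proportions. Assume proportional hazards, with 86% and 56% as the cumulative flare risks over follow-up. Then HR = ln(1 − 0.56) / ln(1 − 0.86) = 0.418. Expected events at 41.8 per arm are 41.82 × (0.86 + 0.56) = 59.4. By the Schoenfeld formula, power = Φ(√59.4 / 2 × |ln 0.418| − 2.241) = Φ(1.12), about **87%**. This gives the lost 18% no weight at all.

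**The case against.** The strongest reply is that nothing of consequence is wrong. It has four parts.

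- **The gap against the claimed power is tiny.** The protocol claims 80%, not the 80.9% that 43 per arm delivers. Against 80% the deficit is 0.4 percentage points, or 42.17 − 41.82 = 0.35 of a child per arm. This stands, and it sets the size of the point. Comparing 79.6% with 80.9% would overstate it.
- **The multiplication by 1.18 is not shown.** A reader might infer that the sponsor multiplied where it should have divided. The match is suggestive, but the protocol states no inflation formula, and step 7 gives another route to the same figures. The shortfall does not depend on the route.
- **The planned analysis is more powerful than the sizing test.** A reader might infer that the flare endpoint has no slack and is underpowered at 102. The protocol does not support that. Under the assumptions of step 8, the log-rank test keeps about 87% power at 41.8 per arm, and it would also use follow-up from lost children up to censoring. This stands as a reason not to change the sample size, but it does not make the sentence in section 9.6 correct, because that sentence refers to the two-proportion calculation.
- **The 0.025 level is not part of the problem.** A reader might infer that a fixed split of alpha between the co-primaries is a fault because it costs power. It is a valid way to control the overall error rate, and the final testing procedure may be set out in a statistical analysis plan that is not at hand.

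What remains after these replies is the literal inconsistency between 43 per arm, 18% loss and 51 per arm.

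**Conclusion.** The point holds as a minor internal inconsistency. At 18% loss, 102 children satisfy the o-SCORAD calculation but not the flare calculation as the protocol sets it up. The shortfall is about 1.2 children per arm against the stated 43. In randomised children it is two in total if the target is 80% power (104), or four if the target is 43 per arm (106). These figures assume that the 18% applies equally to both arms and that lost children contribute nothing, which is how section 9.6 itself uses the loss rate. The 87% log-rank figure rests on proportional hazards and is an indication, not a replacement calculation.

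The result does not support a claim that the trial is underpowered or that more children should be randomised.

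**What to change.** Keep 102 and reword section 9.6, choosing one of two statements for flare:

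- 51 per arm leaves the required 43 evaluable children provided loss does not exceed 15.7%; or
- with 18% loss, about 42 per arm remain, giving about 79.6% to 79.8% power for a fall from 86% to 56% on the two-proportion calculation.

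In either case, change 49 to 50 for o-SCORAD so that it agrees with the stated 41 at 18% loss, and amend the closing sentence to match the option chosen. If the first option is used, retention should be monitored against 15.7%, not 18%.

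The cost is two or three sentences and a marginally less favourable stated power or loss tolerance. Recruitment, visits, treatment and analysis are unchanged.

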9.3 Outcome Measures

9.4 Co-Primary Endpoints

- 1. Change in atopic eczema severity between baseline and 12 weeks of treatment, using the o-SCORAD index.
- 2. Time to first significant flare after treatment cessation in the MTX vs CyA groups.

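### If the two co-primaries are finally tested at a fixed two-sided 0.025 each, Holm's step-down would give more power, mainly for the flare endpoint, at the same 5% family-wise error

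*Protocol*

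**What the plan says.** Section 9.4 lists two co-primary endpoints: change in o-SCORAD from baseline to 12 weeks, and "Time to first significant flare after treatment cessation in the MTX vs CyA groups".

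Section 9.6 sizes them separately.
- For o-SCORAD: "The study aims to detect a difference of 8 o-SCORAD points, assuming a standard deviation (SD) of 10". It arrives at "a sample size of 41 per group, increasing to 49 per group to allow for an estimated 18% loss to follow up", which "will be required to provide 90% power using a t-test with a 0.025 two-sided significance level".
- For flare, 43 per group (51 after allowing for loss) gives 80% power for 86% against 56%, "using a two-sided test with a 0.025 significance level".

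The total is 102, or 51 per arm.

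Section 9.7 gives the analyses: ANCOVA for o-SCORAD; Kaplan-Meier curves, a log-rank test and survival regression for flare. It attaches no significance level and no decision rule to either. Sections 9.1 and 9.7 leave the full methods to a separate SAP. The protocol names no multiplicity procedure.

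**The concern.** Two tests at 0.025 add up to 5%, so the levels in section 9.6 amount to an equal Bonferroni split. If each test stays at 0.025 whatever the other shows, a flare p-value of, say, 0.03 would miss significance even beside a clear 12-week result, and the reverse also holds.

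Holm's procedure tests the smaller p-value at 0.025 and, if that is significant, the other at 0.05. It controls the family-wise error at 5% under any dependence between the tests. It rejects whenever the fixed split rejects, and sometimes when the split does not. The fixed split therefore buys no extra family-wise protection for the power it gives up.

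The loss falls mainly on flare. That is the endpoint with the lower planned power (80% against 90%), and section 9.6 justifies it by its possible influence on prescribing.

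**Working it through.** **Inputs (section 9.6).** o-SCORAD: difference 8, SD 10, n = 41 per arm. Flare: 86% against 56%, n = 43 per arm. Each is at two-sided 0.025. The correlation between the two test statistics is not given; it is taken as 0 first and then varied.

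**Step 1: reproduce the plan's figures.**
- o-SCORAD, two-sample t-test: non-centrality = 8 / (10 × √(2/41)) = 3.62 on 80 degrees of freedom, critical value 2.284. Power is 90.7% at n = 41 and 89.9% at n = 40, so 41 reproduces.
- Flare, pooled two-proportion test without continuity correction: the mean proportion is 0.71, so the null standard error is √(2 × 0.71 × 0.29 / 43) = 0.0979. The alternative standard error is √((0.86 × 0.14 + 0.56 × 0.44) / 43) = 0.0924. Power = Φ((0.30 − 2.241 × 0.0979) / 0.0924) = 80.9% at n = 43. At n = 42 it is 79.8%, so 43 reproduces.

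**Step 2: power at 0.05.** The same formulas give 94.7% for o-SCORAD and 87.9% for flare.

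**Step 3: Holm under independence.** Let P be power at 0.025 and Q power at 0.05, with subscript 1 for o-SCORAD and 2 for flare.
- Flare: P2 + (Q2 − P2) × P1 = 0.809 + (0.879 − 0.809) × 0.907 = 0.873.
- o-SCORAD: P1 + (Q1 − P1) × P2 = 0.907 + (0.947 − 0.907) × 0.809 = 0.940.
- Both: P1Q2 + P2Q1 − P1P2 = 0.830, against P1P2 = 0.734 for the fixed split.
- At least one: 1 − (1 − 0.907)(1 − 0.809) = 0.982 under either rule, because Holm's first step is also at 0.025.

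At 41.8 per arm (51 × 0.82), flare goes from 79.6% to 86.4% and both from 72.7% to 82.5%.

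**Step 4: sensitivity of the gain.**

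| Setting | Flare gain (points) | Gain for both (points) |
|---|---|---|
| 41 and 43 per arm, independent | 6.4 | 9.6 |
| Correlation −0.3 to +0.5 (simulated) | 6.7 to 5.9 | 10.0 to 7.9 |
| Log-rank, Freedman, independent | 5.6 | 8.5 |
| Log-rank, Schoenfeld, independent | 4.4 | 7.5 |

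The log-rank rows assume proportional hazards, with hazard ratio ln(0.44)/ln(0.14) = 0.418 and 43 × (0.86 + 0.56) ≈ 61 events. They use 43 per arm for both endpoints.

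The flare gain also depends on the chance that o-SCORAD is significant at 0.025. With the two-proportion test and independence it is (0.879 − 0.809) × P1:

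| True o-SCORAD difference | P1 | Flare gain (points) |
|---|---|---|
| 8 | 90.7% | 6.4 |
| 6 | 66.7% | 4.7 |
| 4 | 32.3% | 2.3 |
| 2 | 8.9% | 0.6 |
| 0 | 2.5% | 0.2 |

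**Step 5: error rate.** With independent tests, Holm's simulated family-wise error is 0.049 when neither effect exists. It approaches 0.050 when one effect is very large and the other is nil.

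**The case against.** The strongest reply is that no fixed-split decision rule is written. Both 0.025 levels are sample-size inputs, section 9.7 states no level, and sizing at 0.025 is what a Holm analysis would also need for its first step. The SAP, not shown here, may already specify Holm. This stands: a reader might infer that the protocol fixes plain Bonferroni, but the text does not go that far. The loss is conditional on the 0.025 levels being carried unchanged into the final tests.

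A reader might also infer that the trial must win both endpoints, which would make the gain of almost 10 points for both the headline. No section says so; sections 2.3 and 9.4 simply list two objectives and two endpoints. If both were required for success, each could be tested at 0.05 with no split, and Holm would not be the remedy.

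Nor is the independence figure a fixed one. The background in section 2.1 reports that the earlier paediatric comparison of the two drugs found no significant difference (while calling it underpowered), and section 2.4.2 states equipoise. A true 12-week difference below 8 points is therefore plausible, and the flare gain shrinks with it.

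Finally, the equal split is valid and simple, the trial is sized for it, and it keeps tests and 97.5% intervals in agreement. All of that is true. What remains is that Holm gives the same family-wise protection, never rejects less, and needs no patients.

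**Conclusion.** The point holds as a conditional efficiency improvement, not as an error in the protocol. Type I error is controlled under the equal split, and the stated sample sizes reproduce.

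If each final test is held at 0.025, the power forgone on the protocol's own inputs under independence is about 6 points for flare, 3 for o-SCORAD and almost 10 for both. With the planned log-rank test the figures are about 4 to 6 for flare and 7.5 to 8.5 for both. With positive correlation up to 0.5, the gain for both falls to about 8. If the true o-SCORAD difference is 6, 4 or 0, the flare gain is about 5, 2 or nearly 0 points. The chance of at least one significant co-primary is the same either way. If the SAP already uses Holm, there is no loss.

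**What to change.** Leave the sample size and its 0.025 basis in section 9.6 as they are. Add to section 9.7, and to the SAP before unblinding, that the co-primary with the smaller two-sided p-value is tested at 0.025 and that, only if it is significant, the other is tested at 0.05.

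State the one downside in the same place. The protocol gives no interval level for the co-primaries; if 97.5% intervals are shown, a second-step result with p between 0.025 and 0.05 would be significant although its interval includes no effect. Say in advance that the Holm test decides and that the 97.5% intervals are a conservative display.

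The cost is a sentence or two in each document, with no extra patients, data or visits.
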